## 5. Study procedure

### 5.1. Assignment of interventions

Randomization will be centralized and coordinated by the University of Trieste. The randomization list will be generated by a study statistician with Stata 14.2 using block randomization. The list will be implemented in the REDCap® randomization module, which allows centralized allocation of patients through the REDCap® web platform and grants allocation concealment. In each participating center the clinician in charge of the randomization will have secure access to the REDCap® web platform and, after checking whether the study inclusion and exclusion criteria are met, will automatically receive the assignment arm for the enrolled patient. This is an open-label trial, therefore, both the clinician and the patient will be aware of the assigned treatment.

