## 3. Study design

This study is a phase 3 adaptive randomized controlled trial (2 parallel arms, allocation ratio 1:1) implemented during a massive epidemic emergency. Adaptation is a carefully considered

investigational procedure for modifying study parameters while the trial is ongoing, based on a review of the interim data analyses.(10–12)

Our adaptive trial is a sequential random controlled trial, with 2 interim analyses (K=3). We aim to evaluate the safety and efficacy of two different protocol of steroids therapy in adult patients with severe COVID-19.

The trial adaptive framework includes:

- a) a 3-stage sequential O'Brien and Fleming design;
- b) sample size re-calculation at each stage;
- c) binding stopping rule for efficacy according with preplanned critical values;
- d) binding stopping rule for futility according with a preplanned critical values.

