#### 4.6. Schedule of assessments

Time-line	Activity/Treatment	Measurements
Day 1	Consent obtained; randomization; study drug administration by randomized group; vital signs monitoring.	SpO 2 (%), PaO 2 (mmHg), CRP (mg/L), PaO 2 /FiO 2 (mmHg)*, baseline data collection §
Day 3	Treatment continued, as defined above	CRP (mg/L), Worst daily PaO 2 /FiO 2 (mmHg)*, WHO clinical progression score
Day 7	Treatment continued, as defined above	CRP (mg/L), Worst daily PaO 2 /FiO 2 (mmHg)*, WHO clinical progression score

Day 14	Treatment continued, as defined above	CRP (mg/L), Worst daily PaO 2 /FiO 2 (mmHg)*, WHO clinical progression score
Day 28		Patient's outcome determined (mortality, total days of mechanical ventilation, days of invasive mechanical ventilation, days of noninvasive mechanical ventilation) and final data collection °
Hospital discharge		Patient's outcome determined (mortality, days of hospitalization)

\* The type of respiratory support (low-flow oxygen therapy, HFNC, NPPV, IMV, ECMO) under which the PaO2/FiO2 is obtained must be always specified in the appropriate section of the data collection form.

[figure not shown]
§ Baseline data should include:

- a) Date of birth
- b) Sex
- c) BMI
- d) Smoke (yes/no/former)
- e) Date of the onset of symptoms
- f) Date of hospitalization
- g) Date of randomization
- h) Type of respiratory support at randomization (i.e., low-flow oxygen, HFNC, NPPV)
- i) Comorbidities (COPD, Bronchiectasis, Asthma, Other respiratory disease, Pre-existing Diabetes, Atrial fibrillation, Coronaropathy, Chronic heart failure, Other relevant disease of the heart and large vessels, Pulmonary embolism/chronic thromboembolism, Other conditions requiring long-term anticoagulation, Systemic hypertension, Autoimmune Disease, OSA/OHS, Chronic Kidney Disease, Minor stroke, History of Cancer)

°Other data to be collected:

- a) Date of treatment initiation
- b) Date of full-dose treatment completion
- c) Date of de-escalation completion
- d) Deviation from protocol (yes/no; if yes, date of deviation and reason for deviation)
- e) Remdesivir (yes/no)
- f) Anticoagulation:
  - LMWH (prophylactic/anticoagulant)
  - Unfractionated heparin
  - Warfarin

- NOAC

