## 6. Statistical plan

### 6.1. Sequential design procedures

This is a sequential open label randomized clinical trial with 2 interim analyses ( $K=3$ ) with unblinded sample size recalculation (adaptive sample size), stopping rule for early efficacy and stopping rule for futility according to O'Brien and Fleming sequential study design. Stopping rule for either futility or efficacy are bound to specific error spending function according to a Fisher's exact test calculated on primary outcome.

The experimental hypothesis of the study is that treatment with MP improves 28-day survival from 77% in arm 2 to 87% in arm 1 (i.e. risk difference 10%). If this hypothesis is true, the study has a one tail alpha-error  $<0.025$  and an overall power  $>90\%$  by using a Fisher's exact test and critical alpha and beta error value for type I and type II error spending function.

Preplanned critical values and plots are reported in table 1 and figure 1, respectively.

[figure not shown]

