## 6.2. Sample size

Minimum and maximum sample size will significantly change according to the observed effect within the trial sample (expected **average** sample size is between 200 and 680 participants, figure 2). In particular, we expect to enroll 100 participants per arm at the first stage and then between 15 and 175 per arm for each eventual stage if the stopping rules were not met. The actual number of new participants in each arm will be calculated according to the maximum likelihood estimates on observed efficacy at each interim analysis with an overall conditional power for next stage equal to 90%. This approach allows either to minimize the number of enrolled participants if the experimental hypothesis is too conservative or to have a good power level if the experimental hypothesis is too optimistic. The average sample size with relative power and the overall probability for meeting stopping rules according to different level of efficacy of arm 1 vs. arm 2 are reported in figure 2 and figure 3, respectively.

	$H_0: \pi_T - \pi_C = 0$			
Critical values	Stage 1	Stage 2	Stage 3	
Reject H0 (Efficacy)	3.421	2.419	1.975	1.975
Accept H0 (Futility)	-0.695	1.002	1.975	1.975
Information rate	0.333	0.667	1	1
alpha spent	0.0003	0.0079	0.025	0.025

*Table 1 Preplanned critical values (Fisher test) for application of early stopping rules*

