**K = 3; alpha = 0.025, one-sided, binding futility = (-0.695, 1.002), Delta = 0 (O'Brien and Fleming design).**

Figure 1 Plot for application of early stopping rule. Uncertainty area (i.e.  $H_0$  is neither accepted nor rejected) lies above the green line and below the red lines

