### 6.3. Analysis of efficacy (primary outcome)

Interim analyses and final analysis will be carried out by taking into account the potential effect of each individual component of the adaptive design. The interim analyses will provide:

- a) estimate of efficacy as risk difference and relative 95% CI
- b) criteria for stopping rules
- c) if the stopping rules are not met the analysis will provide the number of participants to be randomized for the subsequent stage in each arm.
- d) final analysis will provide efficacy as difference estimate of efficacy as risk difference and relative 95% CI

Subgroup analyses will be carried out if the sample size will allow to. In this case, the following groups will be taken into consideration:

- a) Patients requiring only oxygen therapy, either low-flow or high-flow (HFNC) during the study period
- b) Patients requiring only low-flow oxygen therapy during the study period;

- c) Patients requiring high-flow oxygen therapy (HFNC) but not ventilatory support during the study period
- d) Patients requiring mechanical ventilation, either invasive or noninvasive during the study period
- e) Patients requiring noninvasive mechanical ventilation but not invasive mechanical ventilation during the study period
- f) Patients requiring invasive mechanical ventilation during the study period.

All the analyses will be conducted by the trial statisticians following the intention-to-treat principle.

In case of deviations from the study protocol, such as cross-over between arms, sensitivity analysis will be carried out (eg., *per protocol* analysis).

[figure not shown]

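### No stratification by respiratory support at randomization is stated and the primary test is unadjusted: a small, avoidable loss of precision and credibility, not an error-rate problem

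*Protocol*

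**What the plan says.** Section 3 sets the design as "2 parallel arms, allocation ratio 1:1". Section 5.1 is the whole account of allocation. There is one list, "generated by a study statistician with Stata 14.2 using block randomization", loaded into the REDCap module, and the clinician receives the arm after an eligibility check. No stratification factor is named there or elsewhere in the protocol.

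Section 4.6 lists among the baseline data "Type of respiratory support at randomization (i.e., low-flow oxygen, HFNC, NPPV". Section 4.2 admits patients on the basis of hypoxaemia or of being on HFNC, CPAP or NPPV, so the mix is wide. Section 4.4 moves patients up the support ladder when the previous step fails.

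Section 6.1 ties efficacy and futility stopping to Fisher's exact test, with no covariate or stratum, under the hypothesis that "treatment with MP improves 28-day survival from 77% in arm 2 to 87% in arm 1". On size, section 6.2 states "we expect to enroll 100 participants per arm at the first stage", "then between 15 and 175 per arm for each eventual stage if the stopping rules were not met", with the later numbers set from the effect observed so far. The only adjustment described is in section 6.4: age and sex, for secondary outcomes, if the groups are unbalanced.

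The subgroups in section 6.3 are all about respiratory support, but support over the course of the trial, for example "Patients requiring only oxygen therapy, either low-flow or high-flow (HFNC) during the study period".

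**The concern.** Support level at entry is collected in three categories and, by the protocol's own escalation rule, is higher in patients who failed a simpler form of support. As written, neither the allocation nor the primary test uses it. Balance on a recognised severity marker is left to chance, and any imbalance that occurs stays in the estimate.

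Three things are at stake, all modest. Part of the outcome variance could be removed and is not. A visible imbalance in an open-label trial invites doubt about the result. And because each next stage is sized from the observed effect, a chance shift in case mix carries through to the number recruited.

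**Working it through.** **Inputs from the protocol.** Survival 77% against 87%; 100 per arm at the first look; efficacy bounds 3.421, 2.419, 1.975 and futility bounds -0.695, 1.002 (Table 1); information rates 0.333, 0.667, 1.

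**Assumptions, not in the protocol.** Share on CPAP/NPPV at randomization, p = 30-50%. Difference in 28-day mortality between these patients and the rest, c = 10-25 points.

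**1. The plan's own figures.** The efficacy bounds follow 1.975/√t, which gives 3.421, 2.419 and 1.975. Integrating the three-stage normal statistic with binding futility gives cumulative one-sided alpha of 0.0003, 0.0079 and 0.0250. Table 1 reproduces.

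**2. Size of chance imbalance at 100 per arm.** SD = √(2p(1-p)/100).
- p = 0.3: √(0.42/100) = 6.5 points
- p = 0.5: √(0.50/100) = 7.1 points

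The exact probability of a difference of 10 points or more (hypergeometric, equal arms) is 16% at p = 0.3 and 20% at p = 0.5. A plain normal tail gives 12% and 16%. It is too low because the difference moves in steps of 2 points, and a continuity correction restores 16% and 20%. At 340 per arm the exact figures are 0.6% and 1.1%.

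**3. Effect on the estimate.** Shift = imbalance × c. For a 10-point imbalance this is 0.10 × 10 = 1.0 to 0.10 × 25 = 2.5 points. The null standard error is √(2 × 0.77 × 0.23/100) = 5.95 points, so the shift is 1.0/5.95 = 0.17 to 2.5/5.95 = 0.42 standard errors.

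**4. Share of variance explained.** Fraction = p(1-p)c² divided by the outcome variance.
- Low end: 0.3 × 0.7 × 0.10² = 0.0021; over 0.77 × 0.23 = 0.1771 this is 1.2%.
- High end: 0.5 × 0.5 × 0.25² = 0.0156; over 0.1771 this is 8.8%, and over 0.82 × 0.18 = 0.1476 (mean of the two planned rates) 10.6%.

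So roughly 1-11%. Against a fixed-design reference of 309 per arm (77% v 87%, 90% power, one-sided 0.025), that is worth about 309 × 0.012 = 4 to 309 × 0.106 = 33 patients per arm.

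**5. Type I error.** Simulating the unstratified first-stage test under the null, with survival differing between the two severity groups (400,000 runs per scenario), gives a rejection rate of 0.0002-0.0003 against a nominal 0.0003. There is no inflation.

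**6. Stopping at the first look, given an unlucky 10-point imbalance and a strong factor (shift 2.4 points).** Under 77% v 87% the standard error is √((0.1771 + 0.1131)/100) = 5.39 points.
- Efficacy: 1-Φ(3.421 - 10/5.39) = 6% becomes 1-Φ(3.421 - 12.4/5.39) = 13% if the imbalance favours methylprednisolone.
- Futility: Φ(-0.695 - 10/5.39) = 0.5% becomes Φ(-0.695 - 7.6/5.39) = 1.8% if it favours dexamethasone.
- Efficacy under the null: 0.03% becomes about 0.13%.

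**7. Next-stage size (illustration).** Assume stages 1 and 2 are weighted equally, pooled survival is 82%, and conditional power of 90% is sought at the 2.419 bound. With observed difference d, Z₁ = d/√(0.2952/100) and n = (2.419√2 - Z₁ + 1.282)² × 0.2952/d².
- d = 10 points: 242 per arm, capped at 175; d = 11: 175; d = 12.5: 109.
- d = 12 points: 128 per arm; d = 14.5: 58.

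A 1.0-point shift from 10 changes nothing because of the cap. A 2.5-point shift changes the stage noticeably.

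**The case against.** The case against is strong on several points.

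- **Silence.** Section 5.1 never says the list is unstratified; strata may be fixed in a document not shown. This stands as a caution. Strata must, however, exist before the list does, and the primary test is stated without them.
- **Error rates.** A reader might infer that imbalance makes early stopping unsafe or inflates alpha. The documents do not support that. Chance imbalance is part of the sampling error that the test allows for, and step 5 confirms it. The first-look bounds are also wide: efficacy needs an observed difference of about 17 points.
- **Main prognostic factor.** A reader might take support to be the dominant predictor of death. The protocol does not say so. Section 2.1 reports that the steroid effect differed by support level in an earlier trial, which is effect modification. Excluding invasively ventilated patients also narrows the range.
- **Subgroups.** Stratifying would not guarantee balance in the planned subgroups, which are defined by events after randomization.
- **Timing.** Support is a day 1 item, but section 5.1 does not require it to be entered before the arm is released.
- **Scale.** A shift of 0.17-0.42 standard errors, in the unlucky case only, is small beside ordinary sampling error, which also drives the next-stage size far more.

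All of this limits the point to precision and credibility. It does not remove it: the factor is available at entry, is tied to severity, and as described goes unused.

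**Conclusion.** The point holds as a minor design improvement. The protocol states blocked allocation without a stratum and an unadjusted primary test, while collecting a three-level severity marker at randomization. No stated figure is wrong, and the error control in Table 1 reproduces.

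The size is modest: about 1-11% of the variance of the risk difference, and a 16-20% chance at 100 per arm of an imbalance that moves the estimate by 1.0-2.5 points. Both depend on the assumed share (30-50%) and mortality contrast (10-25 points). With a 20% share, the chance of a 10-point imbalance falls to 11%. By 340 per arm the problem has almost gone.

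**What to change.** In section 5.1, generate the central list in three strata by support at randomization (low-flow oxygen; HFNC; CPAP/NPPV), with permuted blocks of varying size. Say explicitly that CPAP belongs with NPPV, since section 4.2 names it and the baseline item does not. If the list is already stratified, state the factors. Centre need not be a stratum.

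In section 6.3, prespecify a risk difference stratified by or adjusted for this factor. Stratifying the list alone is not enough, because an unadjusted test would not credit the reduced variance. There are two acceptable routes:
- make the stratified analysis primary, keep the boundaries, and rerun the simulations for the stratified test; or
- keep Fisher's exact test as primary and report the stratified estimate as supportive.

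Cost: a regenerated list, one REDCap field completed before allocation, and up to two more incomplete blocks. If the primary test changes, the power simulations must also be rerun and sections 6.1 and 6.2 revised to match. At the planned rates the first look has about 23 + 13 = 36 deaths over three strata, so the stratified method should be one that tolerates sparse cells. If recruitment has begun, the supportive analysis alone is still worth having.

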### 5.2. Data collection and management

A clinical database using REDCap® trial data management system will be developed with a web hosting facility. Electronic case report forms (eCRFs) will be developed to collect all clinical and laboratory related information. The trial database will include baseline information, information on demographics (age, gender), underlying illnesses, baseline and follow-up clinical and laboratory data for the purpose of assessment of clinical outcome. All data queries and corrections will be jointly conducted by the study team prior to database lock. The study team at the University of Trieste, Centro di Riferimento Oncologico of Aviano, and the Institute for Infectious Diseases “L. Spallanzani” of Rome will manage the data and will conduct quality control of the data. All analyses performed, the Clinical Study Report(s) and the final data set will be archived together according to the standard operating procedures and the guidelines of the University Hospital of Cattinara.

## 6. Statistical plan

### 6.1. Sequential design procedures

This is a sequential open label randomized clinical trial with 2 interim analyses ( $K=3$ ) with unblinded sample size recalculation (adaptive sample size), stopping rule for early efficacy and stopping rule for futility according to O'Brien and Fleming sequential study design. Stopping rule for either futility or efficacy are bound to specific error spending function according to a Fisher's exact test calculated on primary outcome.

The experimental hypothesis of the study is that treatment with MP improves 28-day survival from 77% in arm 2 to 87% in arm 1 (i.e. risk difference 10%). If this hypothesis is true, the study has a one tail alpha-error  $<0.025$  and an overall power  $>90\%$  by using a Fisher's exact test and critical alpha and beta error value for type I and type II error spending function.

Preplanned critical values and plots are reported in table 1 and figure 1, respectively.

[figure not shown]

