#### 6.5. Software for simulation and analysis

Study design, simulations, interim analysis and final analysis of primary outcome will be carried out by ICON ADDPLAN V 6.1. This is a proprietary statistical package that contains approved algorithm for dealing with the adaptive design according to EMA and FDA standards. The analysis of secondary outcomes will be carried out at the end of the trial and will be carried out by STATA V.15.

**Figure 2 Adaptive sample size and power.** The yellow bars represent the number of patients to be enrolled in the trial. Red dotted line shows the study power (i.e. the probability to detect a real difference between arm 1 and arm 2 if arm 1 is superior to arm 2 is). Simulation has been carried out assuming 1:1 ratio between arms; first analysis is carried out at 200 patients; adaptive sample size between 30-350 and p-value calculated according Fisher exact statistics conditional power for next analysis 90%; K=3 (i.e. 2 interim analysis and one final analysis).

**Figure 3 Cumulative probability of trial termination.** Continuous lines show the cumulative probability of **early termination** either at first (green line) or second (yellow line) interim analysis. Early termination at both stages can be driven either by efficacy (i.e. reject H0) or futility (i.e. accept H0). The red dotted line shows the cumulative probability to **termination for futility** regardless the stage of analysis (i.e. at first interim, second interim or final analysis).

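### If Fisher's exact test is applied stage by stage, it uses about half of the 2.5% alpha; Boschloo's exact test in its place lifts power from about 90% to about 94%

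*Protocol*

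**What the plan says.** Section 6.1 binds both stopping rules to error spending "according to a Fisher's exact test calculated on primary outcome". The hypothesis is that methylprednisolone "improves 28-day survival from 77% in arm 2 to 87% in arm 1 (i.e. risk difference 10" points). The alpha and power claims, below 0.025 one-sided and above 90%, are made "by using a Fisher's exact test and critical alpha and beta error value for type I and type II error spending function". Table 1 in section 6.2 is titled "Preplanned critical values (Fisher test) for application of early stopping rules". It gives efficacy bounds of 3.421, 2.419 and 1.975, futility bounds of -0.695 and 1.002, and information rates of 0.333, 0.667 and 1. The Figure 1 caption makes futility binding.

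The stage sizes are "100 participants per arm at the first stage and then between 15 and 175 per arm for each eventual stage", re-sized at each interim to 90% conditional power at the maximum likelihood estimate. The Figure 2 caption in section 6.5 confirms that the planning simulation used Fisher p-values. The protocol does not say whether the test at stages 2 and 3 uses the new patients only or all patients so far, nor how stage results are combined.

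**The concern.** The Table 1 bounds spend 2.5% when the statistics are continuous normal z-values. A Fisher p-value from a two-by-two table is discrete and on average too large. If one is computed in each of three separate stages and the three are combined, the shortfall enters three times. The trial then pays in patients for a 2.5% test but runs a stricter one. What is at stake is a few points of power at the design effect, more at smaller effects, and a power figure that sits at its stated limit.

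**Working it through.** **Inputs from the protocol.** Survival 77% versus 87%; 1:1 allocation; 100 per arm, then 15 to 175 per arm per stage; the Table 1 bounds; binding futility; 90% conditional power at the maximum likelihood estimate.

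**Assumption.** Inverse-normal combination of stage-wise p-values with equal weights. It is inferred from unblinded re-sizing together with fixed, equally spaced information rates, although stage sizes may vary from 15 to 175.

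**Table 1 first.** 1.975 × √3 = 3.421 and 1.975 × √1.5 = 2.419, so the bounds have the O'Brien-Fleming shape. Numerical integration with normal z-values and binding futility gives cumulative alpha 0.0003, 0.0079 and 0.0250, as printed. Table 1 is correct.

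**Formulas.** With p_k the one-sided p-value from stage k alone:
- z_k = Φ⁻¹(1 − p_k)
- Z_2 = (z_1 + z_2)/√2
- Z_3 = (z_1 + z_2 + z_3)/√3
- Stage 2 size per arm = (√2 × 2.419 − z_1 + 1.282)² × [p̂_1(1 − p̂_1) + p̂_2(1 − p̂_2)] / (p̂_1 − p̂_2)², limited to 15 to 175. For stage 3, √3 × 1.975 − z_1 − z_2 replaces the first two terms in the bracket.

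**The plan's own figures.** Simulation (1,000,000 trials per scenario; 300,000 for the sample-size grid) with Fisher p-values gives power 90.3% at 77% versus 87%, against the stated >90%. The largest average sample size is about 671, reached at a difference of 6.5 points, against the stated 680 (671/680 = 98.7%).

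**True type I error with stage-wise Fisher.**
- Common survival 77%: 1.38% (1.38/2.5 = 55% of the nominal level)
- 82%: 1.29% (52%)
- 87%: 1.16% (47%; runs of this case vary between about 1.1% and 1.2%)

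**Changing only the stage-wise test,** with re-sizing driven by that test's own z:

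| Stage-wise test | Power, 77% vs 87% | Power, 77% vs 84% | Type I error at 77% | Average N, 77% vs 87% | Average N, no effect |
|---|---|---|---|---|---|
| Fisher | 90.3% | about 60% | 1.38% | 568 | 481 |
| Boschloo | about 93.5% | about 66% | about 2.1% | about 551 | about 501 |
| Mid-p | 94.7% | about 70% | about 2.4% | 545 | about 515 |

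If re-sizing stays driven by the Fisher z, Boschloo reaches 94.2% and mid-p 95.5%. Over common survival rates from 30% to 95%, the largest type I error found was 2.21% for Boschloo and 2.46% for mid-p. If futility is not treated as binding, Boschloo gives about 2.2% and mid-p about 2.6%.

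**The other reading.** With Fisher applied to all patients so far at each look, type I error is about 2.2% and power about 95% (94.9%). That test has no built-in protection when later stage sizes depend on unblinded interim results: the mid-p version of the same cumulative test came out at 2.6%.

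**Margin.** The protocol gives no rate of missing day-28 outcomes. If 3% or 5% were missing (assumed), stage-wise Fisher power would be 89.3% or 88.4%.

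**The case against.** The strongest reply is that nothing here is misstated. Alpha below 0.025 and power above 90% are both true, the simulation already used Fisher p-values, and an exact test is a defensible choice in an open-label trial with unblinded re-sizing. All of that stands.

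The second reply is that stage-wise use is nowhere stated. Section 3.1 speaks of repeated comparisons on accrued data, which could describe a cumulative test, and under that reading the loss nearly disappears. Agreement with the stated figures does not settle it: cumulative Fisher also exceeds 90% power and peaks at an average of about 666, and stage-wise mid-p peaks at about 680. This also stands, and the size of the point is conditional on it.

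A reader might go further and infer three things that the documents do not support:
- That Fisher makes the trial enrol more patients than needed. This is so only near the design effect. Under no effect, Boschloo and mid-p enrol more, because fewer trials stop for futility at stage 1.
- That futility is triggered more often than planned. The planning itself used Fisher, so its futility rate is part of the plan.
- That any less conservative test brings 95% power. Mid-p does, but its level is not guaranteed. Boschloo stops at about 94%.

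**Conclusion.** This is a worthwhile low-cost improvement, not a defect in validity. On the stage-wise, equal-weight reading, Fisher leaves about half of the one-sided 2.5% unused and gives 90.3% power. Boschloo gains roughly 3 to 4 points at the design effect (the chance of missing a true 10-point benefit falls from 9.7% to about 6% or 6.5%) and about 6 points at a 7-point effect.

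Boschloo's level is guaranteed: each stage-wise p-value is valid whatever size was chosen for that stage, and a larger z never undoes a rejection, so the 2.5% limit of Table 1 carries over as long as futility stays binding. The result rests on the inferred combination rule and on conditional-power re-sizing as described. It would be unfair to say that the trial certainly wastes half its alpha, or that its stated alpha and power are wrong.

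**What to change.** Before the first interim:
1. State in the protocol, or in the SAP if it is not already there, that each stage's p-value comes from that stage's patients only, and give the combination rule and weights.
2. Replace Fisher by Boschloo's exact test for each stage-wise p-value. Keep Table 1, binding futility, the 15 to 175 limits and the conditional-power rule.
3. Re-run the simulation and restate type I error, power, average sample size and futility probabilities (Figures 2 and 3).

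Mid-p is an alternative (about 95% power, alpha about 2.4%) only if its level is confirmed by simulation, including the case where a futility bound is overridden.

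The cost is wording and a re-simulation. The average sample size rises by about 20 patients under no effect with Boschloo (481 to about 501), or about 35 with mid-p. The stage-wise p-values may have to be computed outside the package named in section 6.5, since the protocol does not show that it offers these tests. If the intended test is cumulative Fisher, the protocol should say so and show how type I error is controlled under unblinded re-sizing.
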